5.6.3.3. Electrocardiogram

Listings will be produced for all ECG data including unscheduled visit data on the SAS. A listing of clinically relevant ECG abnormalities will also be provided.

5.6.3.4. Other Safety Parameters

Descriptive statistics of values and changes from baseline in supplemental oxygen rate, DLCO, FVC and arterial blood gas will be summarized over time on the SAS by treatment group for the entire study period.

5.7. Other Analyses

5.7.1. Pharmacokinetics

Not applicable.

5.7.2. Immunogenicity

Not applicable.

5.7.3. Pharmacodynamics

Not applicable.

5.7.4. Pharmacokinetic/Pharmacodynamic Relationships

Not applicable.

5.7.5. Biomarkers

Biomarker analysis is optional for each participant. A biomarker-specific ICF should be signed prior to collection of any samples for biomarker analysis.

Biomarker samples will be used to generate plasma and serum marker data for computational analyses. These analyses are considered exploratory and the results will be reported separately from the CSR.

Available biomarkers data at time of final database lock will be listed only.

5.7.6. Health Economics

Not applicable.

5.7.7. Other Variables and/or Parameters

Not applicable.

5.7.8. Definition of Subgroups

No subgroup analysis will be performed.

5.8. Interim Analyses

Not applicable.

5.8.1. Data Monitoring Committee (DMC) or Other Review Board

There is no formal efficacy interim analysis for this study. The sponsor DMC (internal DMC) has overall responsibility for safeguarding the interests of participants and will review on regular basis the results of analyses performed by an unblinded internal statistical support group (SSG) independent from the study team. The DMC will provide recommendations to the study team. Outputs needed for DMC meetings will be flagged in list of outputs in this SAP (DPS part 1) and will focus only on baseline characteristics, protocol deviations, concomitant medications and all safety data (adverse events and laboratory data).

6. SUPPORTING DOCUMENTATION

6.1. Appendix 1 List of Abbreviations

AE	adverse event
ALT/SGPT	alanine aminotransferase
ANCOVA	analysis of covariance
AST/SGOT	aspartate aminotransferase
ATC	anatomic and therapeutic class
BMI	body mass index
BSA	body surface area
CI	confidence interval
CL	total systemic clearance
CRF	case report form
CSR	Clinical Study Report
CTCAE	Common Terminology Criteria for Adverse Events
CV	coefficient of variation
DMC	Data Monitoring Committee
DPS	Data Presentation Specifications
ECG	electrocardiogram
eCRF	electronic case report form
EOT	End of treatment
FAS	full analysis set
FDA	Food and Drug Administration
ICH	International Conference on Harmonisation
IQ	interquartile
IVRS	interactive voice response system
IWRS	interactive web response system
LOCF	last observation carried forward
MedDRA	Medical Dictionary for Regulatory Activities
PD	pharmacodynamic(s)
PI	principal investigator
PK	pharmacokinetic(s)
PP	per protocol
SAE	serious adverse event
SAP	Statistical Analysis Plan
SD	standard deviation
SMQs	standardised MedDRA queries
TEAE	treatment-emergent adverse event
WHO	World Health Organization
WHO-DD	World Health Organization Drug Dictionary

6.2. Appendix 2 Changes to Protocol-Planned Analyses

This current SAP presents a simplified version of the previous final SAP covering the analyses to be performed following the Sponsor decision to prematurely terminate the study due to slow enrollment (decision on 26 Sep 2022). Reporting is simplified: all listings and all the analyses already planned and produced for DMC are kept. For efficacy, all parameters will be listed only.

6.3. Appendix 3 Demographics and Baseline Characteristics

The number of participants in each analysis set will be summarized and listed by intervention group, and overall.

Table 7 and **Table 8** present a list of the demographic variables and baseline disease characteristics that will be summarized by intervention group and overall for the SAS.

Table 7 Demographic Variables

Continuous Variables:	Summary Type
Age (years)	Descriptive statistics (N, mean, standard deviation [SD], median and range [minimum and maximum], and IQ range).
Weight (kg)	
Height (cm)	
Body Mass Index (BMI) (kg/m ²)	
Categorical Variables	
Age ([18-25 years, 26-50 years, 51-64 years, and >=65 years])	
Sex (male, female)	Frequency distribution with the number and percentage of participants in each category.
Race ^a (American Indian or Alaska Native, Asian, Black or African American, Native Hawaiian or other Pacific Islander, White, Multiple)	
Ethnicity (Hispanic or Latino, not Hispanic or Latino)	
Region (US, Latin America, Europe)	

^aIf multiple race categories are indicated, the Race is recorded as 'Multiple'

Table 8 Baseline disease characteristics

Continuous Variables:	Summary Type
Time from SAPH diagnosis (months)	
6MWD (m)	
NT-proBNP (ng/L)	
Calculated PVR (dyn.sec/cm ⁵)	
Cardiac Outputs (L/min), mPAP (mmHg), mRAP (mmHg), PAWP (mmHg), LVEDP (mmHg), sPAP (mmHg), dPAP (mmHg), Mixed venous oxygen saturation (%), Cardiac Index (L/min/m ²), sSAP (mmHg), dSAP (mmHg)	Descriptive statistics (N, mean, standard deviation [SD], median and range [minimum and maximum], and IQ range).
Total pulmonary resistance	
Categorical Variables	
PH therapies (ERA, PD5-inhibitors, Riociguat)	Frequency distribution with the number and percentage of participants in each category.
WHO FC (I, II, III, IV)	

For each participant time since SAPH diagnosis (months) will be derived as:

- (Date of randomization – date of diagnosis + 1) / 12

Demographics and baseline characteristics will also be listed on the SAS.

All available hemodynamic parameters should be included, as available in the clinical database.

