5.1.2. Study Day and Relative Day

Study Day 1 or Day 1 refers to the day of randomization. All efficacy and safety assessments at all visits will be assigned a day relative to this date.

Study day or relative day for a visit is defined as:

- Visit date - (date of Study Day 1) +1, if visit date is \geq date of Day 1
- Visit date - Date of Day 1, if visit date $<$ date of Day 1

There is no 'Day 0'

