5.6.1. Extent of Exposure

Exposure will be summarized for the entire study period, by treatment group and overall using the SAS.

The number and percentage of participants who receive study intervention will be summarized. The number and percentage of participants at each dose level will also be summarized by visit.

Descriptive statistics for duration of study intervention (N, mean, SD, median, and range (minimum, maximum)) will be summarized. Participant-[years] of intervention are calculated as [days of intervention/365.25]. Participant-[years] will be presented by intervention group.

Cumulative exposure will be summarized using week categories.

Study intervention duration is defined as (date of last dose of study intervention – date of first dose of study intervention) +1.

Total dose days of intervention is defined as the total number of days that study intervention was administered to the participant (excluding days off study intervention).

The number (%) of participants with a dose adjustment/dose not administered will be summarized by intervention group. Reasons for dose adjustments/doses not administered will also be summarized.

Descriptive statistics will be presented for the following parameters: Maximum Study Treatment Total Daily Dose and Weighted-Average Study Treatment Total Daily Dose (separately for titration and maintenance periods); Individual Total Daily Maintenance Dose of Study Treatment; Maximum Tolerated Total Daily Dose of Study.

The mean daily dose of study treatment is calculated as (sum of total daily dose)/study treatment duration.

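### The SAP divides a day count by 12 to obtain months since SAPH diagnosis, so values programmed as written come out about 2.5 times too large

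*SAP*

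**What the plan says.** Table 8 in SAP Section 6.3 (Appendix 3) includes "Time from SAPH diagnosis (months") as a continuous baseline variable, to be summarized by intervention group and overall on the Safety Analysis Set with N, mean, SD, median, range and interquartile range. Below the table the SAP gives the rule: "For each participant time since SAPH diagnosis (months) will be derived as", followed by "Date of randomization – date of diagnosis + 1) / 12", with the opening parenthesis before the first date. Baseline characteristics are also to be listed by participant on the same set.

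Two other places in the SAP use the same arithmetic form. Section 5.1.2 defines study day as "Visit date - (date of Study Day 1) +1" for visits on or after Day 1. Section 5.6.1 states: "Study intervention duration is defined as (date of last dose of study intervention – date of first dose of study intervention) +1". That section then obtains participant-years from "days of intervention/365.25". The SAP gives no days-to-months conversion, and nothing elsewhere corrects the divisor of 12. Protocol Section 8.1 collects the date of the initial SAPH diagnosis, so the input is a calendar date.

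**The concern.** The label and the formula do not agree in units. The added 1 is the inclusive-day convention, which makes sense only if the numerator counts days. Twelve is the number of months in a year, not the number of days in a month, so it cannot convert days to months.

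The absolute description of the enrolled population is at stake. Under SAP version 3.0 all efficacy parameters are listed only, so the baseline table is one of the few summaries left that tells a reader who was studied. A figure of 30 or 60 months looks plausible for this disease and could pass review unnoticed. Section 5.8.1 places baseline characteristics among the DMC outputs, and Section 5.1 keeps the analyses already produced for the DMC for the final report. If existing code follows the written rule, the error would carry straight through.

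**Working it through.** There is no stated result to reproduce; the check is one of units.

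**Inputs**
- Numerator: D = date of randomization − date of diagnosis + 1, in days (SAP Section 6.3; same form as in Sections 5.1.2 and 5.6.1).
- Claimed unit of the result: months (SAP Section 6.3, both Table 8 and the derivation line).
- Days per year: 365.25 (SAP Section 5.6.1), hence 365.25/12 = 30.4375 days per month.

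**Formulas**
- As written: D/12.
- In months: D/30.4375.
- Ratio of the two: (D/12)/(D/30.4375) = 30.4375/12 = 2.536, whatever D is.

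**Examples**

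| Interval | D (days) | As written, D/12 | Months, D/30.4375 |
|---|---|---|---|
| 1 year | 365 + 1 = 366 | 30.5 | 12.0 |
| 2 years | 730 + 1 = 731 | 60.9 | 24.0 |
| 5 years | 1826 + 1 = 1827 | 152.3 | 60.0 |
| 10 years | 3652 + 1 = 3653 | 304.4 | 120.0 |

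**Sensitivity to the length of a month.** A 30-day month gives 30/12 = 2.50. Months of 28 and 31 days give 28/12 = 2.33 and 31/12 = 2.58. The conversion chosen hardly changes the result.

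**Effect on the summaries.** Because this is a pure scale factor, the mean, SD, median, minimum, maximum and interquartile range are all multiplied by 2.536. The ratio of one arm to the other is unchanged.

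**The other reading.** Suppose the date difference were taken in months. A difference of 36 months gives (36 + 1)/12 = 3.08, which is a number of years. Printed under a months label, that value would be about 12 times too small. The rule and its label therefore conflict on either reading.

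**The case against.** The strongest reply concerns consequence, since the unit slip itself is plain on the page. No code or output is visible, and a programmer may have used a sensible divisor, in which case no reported value is wrong. The variable is one of many in Table 8. It is not a stratification factor, an eligibility criterion or a covariate in the protocol's ANCOVA, and SAP version 3.0 tests no hypothesis and runs no subgroup analysis. A constant factor in both arms leaves their relative comparison intact. The report is a synoptic one for a trial stopped for slow enrollment, and duration can be recalculated from the dates collected. Finally, the SAP states no days-to-months rule, so 30.4375 is an inference.

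Most of this stands as a limit on importance. The inflation does depend on the formula being programmed literally, and no study conclusion turns on it. None of it makes the formula right. If the programmer departed from the text, the SAP no longer documents the derivation that was used, and the text still needs correcting. As for the divisor, 365.25/12 follows from the SAP's own year length, and a 30-day month would give nearly the same answer.

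**Conclusion.** The derivation is wrong as written. Read as a day count, which the added 1 and the SAP's usage elsewhere support, it overstates time since diagnosis by a factor of 2.54 (2.33 to 2.58 across month lengths of 28 to 31 days). Read as a difference in months, it yields years under a months label. The size of the error in reported values assumes that the program follows the SAP literally. The damage is confined to the absolute level of one descriptive baseline variable: relative balance between arms, the efficacy listings and the safety summaries are unaffected. It should be corrected before the final tables are produced, but it does not threaten the trial's conclusions.

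**What to change.** In SAP Section 6.3, replace the divisor of 12 with 30.4375, so that the rule reads (date of randomization − date of diagnosis + 1)/30.4375, and note that 30.4375 = 365.25/12, in line with Section 5.6.1. Check the derivation code, and any baseline table or listing already produced for the DMC, against the corrected rule, and rerun them if they used 12.

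The cost is one constant in the SAP, one line of code and, if needed, a rerun of the baseline outputs. No design element, data collection or clinical decision changes.

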6.4. Appendix 4 Protocol Deviations

In general, the following list of major protocol deviations may have the potential to impact participants' rights, safety or well-being, or the integrity and/or result of the clinical study.

Participants with major protocol deviations will be identified prior to database lock and the participants with major protocol deviations will be displayed by category.

- Developed withdrawal criteria but not withdrawn
- Entered but did not satisfy criteria
- Received a disallowed concomitant treatment
- Received wrong treatment or incorrect dose
- Other

See TV-FRM-04718 "Major Protocol Deviation Criteria" for detailed definitions of major protocol deviations.

A separate listing for all protocol deviations related to COVID-19 will be also produced.

6.5. Appendix 5 Prior and Concomitant Medications

Prior and Concomitant medications will be coded using the last available version of World Health Organization Drug Dictionary (WHO-DD). Prior medications are defined as any therapy used before the day of first dose (partial or complete) of study intervention (including those ongoing at first dose). Concomitant medications are defined as any therapy used on or after the same day as the first dose of study intervention, including those that started before and continue on after the first dose of study intervention.

All prior and concomitant medications will be listed for the SAS.

6.6. Appendix 6 Medical History

All Medical history will be listed for the SAS.

6.7. Appendix 7 Intervention Compliance

Study intervention compliance will be summarized descriptively for the SAS.

The number and percentage of participants who have at least 80% study intervention compliance through the EOMOP period will be summarized by treatment group.

Study intervention compliance will be calculated as follows:

Compliance = [(number of tablets dispensed – number of tablets returned) / total number of tablets that should have been taken during the period] × 100.

Compliance will be also listed.

6.8. Appendix 8 Adverse Events of Special Interest

The following adverse events of special interest will be used for selexipag. These are based on the important identified and potential risks in the latest Risk Management Plan and on-going discussion with Pharmacovigilance Risk Assessment Committee.

AE Special Interest Category
Anaemia
Bleeding events
Gastrointestinal disturbances denoting intestinal intussusception (manifested as ileus or obstruction)
Hyperthyroidism
Hypotension
Light-dependent non-melanoma skin malignancies
Major adverse cardiovascular events (MACE)
Medication errors
Ophthalmological effects associated to retinal vascular system
Pregnancy
Pulmonary venoocclusive disease associated with pulmonary oedema
Renal function impairment / acute renal failure
Prostacyclin associated reactions*

*Prostacyclin associated reactions will be summarized separate from other AESIs

A specific file containing all preferred terms for each category as per last coding version will be maintained.

6.9. Appendix 9 Medications of Special Interest

Concomitant and prior medications of special interest are defined as follows:

Concomitant/Prior Medication Special Interest Category	Standard ATC Name	Note
PAH-specific medications	Sildenafil	Medications with ATC name containing any of the listed standard ATC names are considered as PAH-specific medications.
PAH-specific medications	Tadalafil	
PAH-specific medications	Vardenafil	
PAH-specific medications	Iloprost	
PAH-specific medications	Epoprostenol	
PAH-specific medications	Beraprost	
PAH-specific medications	Treprostинil	
PAH-specific medications	Selexipag	
PAH-specific medications	Riociguat	
PAH-specific medications	Macitentan	
PAH-specific medications	Bosentan	
PAH-specific medications	Ambrisentan	

6.10. Appendix 10 Laboratory Toxicity Grading

The grading scale use for lab assessments is based on tables below.

Blood chemistry marked abnormalities (SI Units)				
Laboratory test name (CDISC Synonym[s])	LL	LLL	HH	HHH
Alanine aminotransferase	NA	NA	$> 3 \times \text{ULN}$	$> 5 \times \text{ULN}$
Aspartate aminotransferase	NA	NA	$> 3 \times \text{ULN}$	$> 5 \times \text{ULN}$
Alkaline phosphatase	NA	NA	$> 2.5 \times \text{ULN}$	$> 5 \times \text{ULN}$
Bilirubin; Total bilirubin	NA	NA	$> 2 \times \text{ULN}$	$> 5 \times \text{ULN}$
Creatinine	NA	NA	$> 1.5 \times \text{ULN}$	$> 3 \times \text{ULN}$
Sodium	NA	$< 130 \text{ mmol/L}$	$> 150 \text{ mmol/L}$	$> 155 \text{ mmol/L}$
Potassium	$< 3.2 \text{ mmol/L}$	$< 3.0 \text{ mmol/L}$	$> 5.5 \text{ mmol/L}$	$> 6.0 \text{ mmol/L}$

CDISC = Clinical Data Interchange Standards Consortium; NA = not applicable; ULN = upper limit of normal.

Blood chemistry marked abnormalities (SI Units)				
Laboratory test name (CDISC Synonym[s])	LL	LLL	HH	HHH
Hemoglobin	$< 100 \text{ g/L}$	$< 80 \text{ g/L}$	$> 20 \text{ g/L above baseline}$	$> 40 \text{ g/L above baseline}$
Hematocrit; EVF; PCV (male)	$< 0.32 \text{ L/L}$	$< 0.20 \text{ L/L}$	$> 0.60 \text{ L/L}$	$> 0.65 \text{ L/L}$
Hematocrit; EVF; PCV (female)	$< 0.28 \text{ L/L}$	$< 0.20 \text{ L/L}$	$> 0.55 \text{ L/L}$	$> 0.65 \text{ L/L}$
Platelets (assuming no platelet cluster)	$< 75 \times 10^9/\text{L}$	$< 50 \times 10^9/\text{L}$	$> 600 \times 10^9/\text{L}$	$> 999 \times 10^9/\text{L}$
Leukocytes; white blood cells	$< 3.0 \times 10^9/\text{L}$	$< 2.0 \times 10^9/\text{L}$	$> 20.0 \times 10^9/\text{L}$	$> 100.0 \times 10^9/\text{L}$
Neutrophils (Abs)	$< 1.5 \times 10^9/\text{L}$	$< 1.0 \times 10^9/\text{L}$	NA	NA
Eosinophils (Abs)	NA	NA	$> 5.0 \times 10^9/\text{L}$	NA
Lymphocytes (Abs)	$< 0.8 \times 10^9/\text{L}$	$< 0.5 \times 10^9/\text{L}$	$> 4.0 \times 10^9/\text{L}$	$> 20 \times 10^9/\text{L}$

CDISC = Clinical Data Interchange Standards Consortium; EVF = erythrocyte volume fraction; NA = not applicable; PCV = packed cell volume.

